#### **7.4.3 Clinical Laboratory Assessments**

Fasted blood samples and urine samples will be collected for the clinical laboratory tests (hematology, biochemistry, coagulation, virology, drugs of abuse, hormones, and urinalysis, [Table 3](#)) following the timing noted in the Schedule of Assessments ([Table 1](#) and [Table 2](#)). Additional laboratory safety examinations during the trial are at the discretion of the Investigator. All blood and urine samples will be worked up and analyzed in Nuvisan's clinical laboratory. Any abnormalities in any of the laboratory parameters will be judged by a physician individually in relation to the reference ranges from the laboratory. In addition, feces samples will be collected.

For all findings with major deviation and/or possible pathological relevance, follow-up examinations will be carried out until the deviation returns to normal or the absence of pathological relevance can be confirmed. If a deviation considered clinically relevant has not returned to a normal or not clinically relevant value when it is checked during the screening laboratory tests, the subject will not be included in the trial.

Laboratory abnormalities considered clinically relevant by the Investigator will be reported as AE. The following parameters will be determined:

**Table 3** Safety Laboratory Evaluations

Biochemistry	Aspartate aminotransferase Alanine aminotransferase Alkaline phosphatase γ-Glutamyl-transferase Lactate dehydrogenase Creatine phosphokinase b Amylase Lipase	Bilirubin (total) a Cholesterol Triglycerides Uric acid	Sodium Potassium Creatinine Urea Glucose
Coagulation	Thrombin Time Activated partial thromboplastin time Hemoclot Thrombin Inhibitor (Anti-Factor II)		
Hematology	Hematocrit Hemoglobin Red blood cell count Mean corpuscular volume Mean corpuscular hemoglobin Mean corpuscular hemoglobin concentration	Platelet count White blood cell count	White blood cell differentials and absolute counts c : Basophiles Eosinophiles Lymphocytes Monocytes Neutrophiles
Urinalysis	pH Nitrite Protein Glucose	Ketone bodies Urobilinogen Bilirubin Urine pregnancy test	White blood cell count Red blood cell count Microscopic examination d
Urine drug screen	Cocaine Amphetamines Methamphetamines Opiates	Barbiturates Benzodiazepines Methadone Cannabinoids	Tricyclic antidepressants Cotinine Ecstasy
Other tests:	Hepatitis B surface antigen Hepatitis B core antibody Hepatitis C antibody HIV1/HIV2 antibodies Follicle stimulating hormone (if applicable) Thyroid stimulating hormone Serum pregnancy test (beta-HCG) eGFR e Breath Alcohol test (at Screening and Admission)		
Feces	Occult blood in feces (Haemoccult)		

HIV = human immunodeficiency virus, HCG = human chorionic gonadotropin

a In case of an increased Bilirubin (total) the direct Bilirubin will be determined.

b In case of an increased creatine phosphokinase (CK), myocardium/brain type (CK-MB) will be determined; if the ratio of CK/CK-MB is above 6, troponin will be determined as well.

c In case of abnormal findings, manual differential blood count can be requested by the Investigator.

d Only if blood, protein, nitrite, or leucocytes are positive on the dipstick.

e Estimated glomerular filtration rate (eGFR) calculated using the Cockcroft-Gault equation.

The Sponsor should receive a list of laboratory normal ranges before shipment of the IMPs. Any change in laboratory normal ranges during the trial should be forwarded to the Sponsor, including laboratory certificates.

For the amount of blood taken in this study, see [Appendix II](#).

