**Table 2 Schedule of Assessments - Period 2 (Administration of Tepotinib and Dabigatran Etexilate)**

Assessment/ Activity	Study Period 2							End of Trial Visit a
	Day 1	Day 2 - 6	Day 7	Day 8	Day 9	Day 10	Day 11	
Hospitalization	X	X	X	X	X	X	X j	
Ambulatory Visits								X
Physical examination								X
Vital signs (blood pressure, pulse rate, body temperature)	X b	X b	X b	X c	X c	X c	X c	X
12-lead ECG	X d	X						
Clinical laboratory (hematology, biochemistry, urinalysis)	X e	X e	X e	X e			X e	X
Coagulation	X i			X i	X i			X
Serum pregnancy test								X
Administration of tepotinib	X f	X f	X f	X f				
Administration of dabigatran etexilate				X f				
PK blood sampling (tepotinib and its metabolites)		X g	X g	X g				
PK blood sampling total dabigatran (unconjugated and conjugated)				X h	X h	X h	X h	
Adverse events	←-----→							X
Concomitant medication	←-----→							X

ECG = electrocardiogram, PK = pharmacokinetics

**Adverse events and concomitant medication will be assessed from screening throughout the whole study until End of trial Visit.**

- a 7 ± 1 days after last drug administration in Period 2 (Day 15).
- b Vital signs (blood pressure and pulse rate) will be measured after at least 5 min rest before each (within 60 min prior to dosing) and 6 h after each tepotinib administration.
- c Vital signs will be measured after at least 5 min rest before (within 60 min prior to dosing) as well as 4, 8, 24, 48 and 72 h after the combined dabigatran etexilate and tepotinib administration.
- d After at least 5 min rest before each time point 12-lead ECGs will be recorded and printed out. Days 1 to 7 within 60 min prior to dosing and 6 h after each tepotinib administration. Day 8 within 60 min prior to dosing, as well as 4, 8, 24, 48 and 72 h after the combined dabigatran etexilate and tepotinib administration.
- e Laboratory assessments will be performed on Day 1, 2, 7 and 8 pre-dose, and on Day 11.

- f On Days 1 to 7, 500 mg tepotinib will be administered together with 240 mL of water 30 min after start of a standardized breakfast (completely consumed within 25 min).  

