### 5.3.1 Inclusion Criteria

To be eligible, the subject must fulfill all the following criteria:

1. Male or female, aged 18 to 44 years inclusive (at Screening)
2. Body mass index (BMI)  $\geq 18.5$  and  $\leq 29.9$  kg/m^2 and body weight between 50 to 100 kg, inclusive (at Screening)
3. A female participant is eligible to participate if she is of non-childbearing potential, confirmed at Screening, by fulfilling at least one of the following criteria:
  - Females who are postmenopausal (age-related amenorrhea  $\geq 12$  consecutive months and increased follicle-stimulating hormone [FSH]  $> 40$  mIU/mL)
  - Documentation of irreversible surgical sterilization by hysterectomy, or bilateral oophorectomy, or bilateral salpingectomy
4. A male participant must agree to use and to have his female partner of childbearing potential to use highly effective method of contraception (ie methods with a failure rate of less than 1% per year) as detailed in the Clinical Trial Facilitation Group (CTFG) recommendations [8] during the period of participation in the study and for at least 3 months after the last investigational medicinal product (IMP) administration (see Appendix III). Males must also refrain from donating sperm during this period and should always use a barrier method such as condom concomitantly. The male participants will be asked to report pregnancies in their female partners up to 3 months after the last IMP intake
5. Subject must be healthy, as assessed by the Investigator, with no clinically significant abnormality identified on physical examination and no active clinically significant disorder, condition, infection or disease that would pose a risk to subject safety or interfere with the study evaluation, procedures, or completion (at Screening and Day -1)
6. Subject must have given written informed consent before any study-related activities are carried out and must be able to understand the full nature and purpose of the study, including possible risks and adverse effects
7. All values for hematology, coagulation, and biochemistry tests of blood and urinalysis within the normal range (at Screening). Minor (solitary) non-clinically relevant deviation(s) are allowed as judged by the Investigator; however, amylase, lipase and alanine-amino-transferase [ALT] or aspartate-amino-transferase [AST] values should not exceed the upper limit of normal (ULN).

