### **5.5.2 Withdrawal from the Trial**

Subjects must be withdrawn from the study by the Investigator at any time for any of the following reasons:

- Subject withdrew consent
- Subject lost to Follow-up
- Participation in another clinical study
- Relevant adverse events (AEs) occur that do not justify the subject's continuation in the study
- Pregnancy
- Protocol noncompliance judged as significant by the Investigator and/or Sponsor
- Use of a non-permitted concomitant drug as defined in Section [6.5](#). However, any medications that are considered necessary for the subject's wellbeing (eg paracetamol up to 1500 mg per day) may be given at the discretion of the Investigator.
- Subject is no longer able to participate for other medical reasons (eg surgery, intercurrent illness).
- Any other condition which to the opinion of the Investigator no longer justifies or permits a safe participation of the subject.
- Any of the following individual stopping criteria is met unless deemed unrelated to study drug by the Investigator with alternate etiology identified:
  - Abnormal clinically relevant vital signs confirmed on 2 or more measurements (min. 5 minute intervals), including abnormal blood pressure
    - hypotension defined as systolic < 80 mmHg and/or diastolic < 40 mmHg, or
    - hypertension defined as systolic > 160 mmHg and/or diastolic > 100 mmHg
  - Abnormal clinically relevant ECG findings, including a corrected QT-interval (ad modus Fridericia; QTcF) > 500 ms or an increase in QTcF > 60 ms compared to baseline, confirmed on  $\geq 2$  repeat measurements.
  - Marked increases in liver or renal parameters (ALT/AST  $\geq 3 \times$  upper limit of normal range (ULN), total bilirubin  $\geq 2 \times$  ULN, creatinine  $> 1.5 \times$  ULN) confirmed by  $\geq 2$  repeat measurements.

- Any clinically relevant symptom or sign which in the opinion of the Investigator and/or Sponsor warrants subject withdrawal
- Coagulation tests that may be associated with an increased risk of bleeding except for thrombin inhibitory effects expected due to dabigatran but not exceeding 3-fold prolongation in the aPTT upper limit of normal at peak.

If a subject has failed to attend scheduled trial assessments, the Investigator must determine the reasons and the circumstances as completely and accurately as possible.

In case a subject should be withdrawn from the trial, the medical monitor and clinical trial leader at the Sponsor will be informed immediately.

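### The troponin rule in Table 3 footnote b runs in the wrong direction: with total CK as numerator, a ratio above 6 triggers troponin when CK-MB is low relative to CK, not when it is high (low priority)

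*Protocol*

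**What the plan says.** Table 3 in Protocol Section 7.4.3 lists creatine phosphokinase under biochemistry and attaches footnote b. When CK is increased, the footnote says that "myocardium/brain type (CK-MB) will be determined", and it continues: "if the ratio of CK/CK-MB is above 6, troponin will be determined as well". It uses CK for creatine phosphokinase and CK-MB for the myocardium/brain type, so the numerator is total CK.

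This is current text. The new wording recorded under Amendment 1 in Appendix IV has the same orientation. Troponin appears nowhere else in the Protocol and not at all in the SAP, whose Section 15.3 only points back to Protocol Section 7.4.3 for the list of tests. Neither document gives units for CK or CK-MB, a reason for the value 6, or another troponin rule.

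The body of Section 7.4.3 adds three general provisions:

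- "Any abnormalities in any of the laboratory parameters will be judged by a physician individually in relation to the reference ranges from the laboratory".
- For findings that deviate strongly or may be pathological, "follow-up examinations will be carried out until the deviation returns to normal or the absence of pathological relevance can be confirmed".
- "Additional laboratory safety examinations during the trial are at the discretion of the Investigator".

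None of the three mentions troponin.

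**The concern.** The footnote describes a two-step cascade: a raised total CK prompts measurement of its myocardial fraction, and the result decides whether troponin is added. Such a sequence would be expected to escalate when the myocardial fraction is high. Other reflex footnotes to Table 3 escalate on the abnormal result: a raised total bilirubin leads to direct bilirubin, and a positive dipstick leads to microscopy. In footnote b the second step does the opposite and switches off as CK-MB rises at a given CK.

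At stake is a safety-monitoring rule, not an estimate. A subject with raised CK and a high CK-MB would get troponin only if a physician asked for it, while a subject with raised CK and a low CK-MB would get it by rule. The trial is the first to give multiple doses of tepotinib to healthy subjects (Protocol Sections 3 and 5.2.3) and relies on close laboratory monitoring, so a mandatory laboratory rule should point the right way.

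**Working it through.** **Inputs**

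- Trigger: CK/CK-MB above 6, total CK as numerator (Table 3 footnote b).
- Meaning of CK-MB: the myocardium/brain type (same footnote and the List of Abbreviations).
- Units: not given. Same units are assumed first, then relaxed.
- The plan gives no derivation of the 6, so there is no figure to reproduce beyond the cut-off itself.

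**Step 1: the rule as a share of CK.** Let s = CK-MB/CK in the same units. Then CK/CK-MB = 1/s, and

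CK/CK-MB > 6 ⇔ s < 1/6 = 16.7%.

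Troponin is automatic below a share of 16.7% and not automatic at or above it.

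**Step 2: does the missing unit change the direction?** Suppose the reported CK-MB figure is k times its value in CK units, with k > 0. The reported ratio is 1/(k·s), which falls as s rises for every k. The switch point is s = 1/(6k):

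- k = 0.5: 1/3 = 33.3%
- k = 1: 1/6 = 16.7%
- k = 2: 1/12 = 8.3%

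These k values are illustrations and do not bound the switch point. Units move the switch point but cannot reverse the direction.

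**Step 3: the printed rule beside two possible repairs.** CK is set to 600 for illustration; the results depend only on the share.

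| CK-MB share | CK-MB | CK/CK-MB | Printed rule (ratio > 6) | Share > 6% | Inequality reversed (ratio < 6) |
|---|---|---|---|---|---|
| 2% | 12 | 50.0 | troponin | no | no |
| 4% | 24 | 25.0 | troponin | no | no |
| 6% | 36 | 16.7 | troponin | no | no |
| 10% | 60 | 10.0 | troponin | troponin | no |
| 15% | 90 | 6.7 | troponin | troponin | no |
| 16.7% | 100 | 6.0 | no | troponin | no |
| 18% | 108 | 5.6 | no | troponin | troponin |
| 20% | 120 | 5.0 | no | troponin | troponin |
| 25% | 150 | 4.0 | no | troponin | troponin |
| 30% | 180 | 3.3 | no | troponin | troponin |

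At both ends (2–6% and 18–30%) the printed rule gives the opposite answer to either repair. The repairs differ in the middle: shares of 10% and 15% trigger troponin as printed and under the 6% rule, but lose it if the inequality is simply reversed.

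**Step 4: frequency.** The documents give no expected rate of raised CK or of a high CK-MB share, so no number of affected subjects can be derived.

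**The case against.** The strongest reply has three parts.

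*The intent is not stated.* The documents do not say what the troponin step is for, and that troponin is a cardiac marker is general knowledge. CK/CK-MB could be loose notation for CK-MB as a percentage of CK, and the single clinical laboratory may already apply it that way. This stands as a caveat: the wrong direction is inferred from the cascade, and no other sentence contradicts the footnote. It does not rescue the text, because nothing in either document redefines the ratio and the laboratory's practice is not described.

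*Other provisions cover the gap.* Follow-up of possibly pathological findings is mandatory, every abnormality is judged by a physician, extra tests are allowed, and the physician sees CK-MB whenever CK is raised. This stands, and it is why the effect is small. These provisions soften the rule without correcting it.

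*The printed rule mostly over-tests.* In the same units, every share below 16.7% triggers troponin. That is true, but the shares left out are the highest ones.

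A reader might infer that troponin is withheld from subjects with a high CK-MB, or that cardiac safety goes unmonitored. The documents do not support either. Section 7.4.3 leaves troponin available at any ratio. Table 2 schedules ECGs on "Days 1 to 7 within 60 min prior to dosing and 6 h after each tepotinib administration", and on Day 8 before dosing and at 4, 8, 24, 48 and 72 h after it. Section 5.5.2 lists "Abnormal clinically relevant ECG findings, including a corrected QT-interval" among the individual stopping criteria. Section 5.3.1 requires normal biochemistry at Screening apart from minor deviations, and Section 6.5.3 bars exhausting exercise. Section 3 reports no clinically significant laboratory or ECG findings in the earlier healthy-subject trials and names lipase and amylase elevations as the identified risks.

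**Conclusion.** Wrong as written, low priority. The only mandatory troponin trigger in the plan is on when CK-MB is a small part of CK and off once it reaches CK/6 (16.7% in the same units). The arithmetic is certain and does not depend on units. Calling it an error rests on one inference: that a cascade ending in troponin is meant to escalate with the myocardial fraction.

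The 16.7% figure assumes matching units. The intended cut-off cannot be recovered from the documents; in particular, it is not established that the sponsor meant 6%. No effect on subject numbers can be quantified, and the sample size, error rates and PK analysis are unaffected.

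**What to change.** Reword footnote b so that the trigger rises with the CK-MB share, for example: *if CK-MB is more than 6% of total CK (both in the same units), troponin will be determined as well.* The sponsor's medical lead should confirm the percentage and the units, since 6% is an assumption.

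Do not simply change the inequality to below 6. That would restore the direction but remove automatic troponin for every share below 16.7%, including the 6–16.7% band that is tested automatically today.

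The cost is one footnote in the next amendment, with no extra visits or scheduled samples. If a laboratory instruction implements the footnote (the documents mention none for this rule), one line there should match. The downside is that subjects below the chosen cut-off no longer get troponin automatically; the Investigator can still order it under Section 7.4.3.

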#### **7.4.4 Vital Signs, Physical Examinations, and Other Assessments**

##### **7.4.4.1 Vital Signs**

Blood pressure (systolic blood pressure [mmHg] and diastolic blood pressure [mmHg]) will be measured according to the oscillometric method using an automated device, which also indicates the corresponding pulse rate (bpm). Blood pressure and pulse rate will be measured after at least 5 min in a supine position, according to the schedule of assessments ([Table 1](#) and [Table 2](#)).

Body temperature will be measured auricular.

Further vital sign measurements during the course of the study are at the discretion of the Investigator.

##### **7.4.4.2 ECG**

Twelve-lead ECGs will be recorded as scheduled in the trial schedule of assessments ([Table 1](#) and [Table 2](#)) using the ECG system (CardioPerfect®, Welch Allyn). The ECGs will be recorded in supine position after at least 5 min rest.

ECGs will be plotted with a paper speed of 50 mm/s and 10 mm/mV amplitude, with 10 seconds recording duration for all leads and at least 3 complexes, but preferably 5 complexes in each lead.

Per time-point, the ECG will be stored electronically, printed and reviewed in a timely manner by the Investigator. The original printout will be stored with the subject's source data. Electronic data may be transferred to a central ECG laboratory for central reading and further analysis; these results would be reported separately.

ECG printouts must be signed and dated by the person evaluating the ECG. The ECG will be interpreted by the Investigator (normal/abnormal). For abnormal ECGs, the clinical significance (yes/no) must be judged by the Investigator and the abnormality is to be specified.

Additional ECGs during the course of the study are at the discretion of the Investigator.

##### **7.4.4.3 Physical Examination**

The physical examination comprises general appearance, skin, head, neck (including thyroid), eyes, ears, nose, throat, abdomen, as well as neurological, peripheral vascular, musculoskeletal, cardiovascular and pulmonary system.

Physical examination will be scheduled according to the study flow chart (see [Table 1](#) and [Table 2](#)). Further physical examinations during the course of the study are at the discretion of the Investigator. Any relevant findings are to be recorded on the Medical History form in the eCRF

(for findings from the past that occurred prior to ICF signature) or on the AE form in the eCRF (for findings presently occurring; events existing but unresolved prior to drug administration).

## 7.5 Pharmacokinetics

### 7.5.1 Blood Sampling

On the PK profiling day, an indwelling venous catheter will be positioned in a suitable forearm vein for blood sampling and should be kept, if possible, until at least 24 h after dosing. After removing the indwelling venous cannula, samples will be taken by venipuncture.

Blood samples will be taken and plasma levels of total dabigatran will be determined as closely as possible to the following time points:

- Day 1 of Period 1 at pre-dose (within 60 min prior to dosing) and 15, 30, 45, 60, 90 min, and 2, 3, 4, 6, 8, 12, 24, 36, 48 and 72 h post-dose, and
- Day 8 of Period 2 at pre-dose (within 60 min prior to dosing) and 15, 30, 45, 60, 90 min, and 2, 3, 4, 6, 8, 12, 24, 36, 48 and 72 h post-dose.

Blood samples will be taken and plasma levels of tepotinib and its metabolites MSC2571109A and MSC2571107A will be determined as closely as possible to the following time points:

- Day 6 of Period 2 at pre-dose (within 60 min prior to dosing), and
- Day 7 of Period 2 at pre-dose (within 60 min prior to dosing) and 15, 30, 45, 60, 90 min, and 2, 3, 4, 6, 8, 12 and 24 h post-dose (prior to dosing on Day 8, within 60 min prior to administration).

The exact date and time of sample collection must be recorded in the eCRF and will be used in the calculation of PK parameters. Blood samples should be taken as close as possible to the scheduled time points. Samples taken outside of the time periods shown in [Table 4](#) need an explanation and will be considered a protocol violation.

**Table 4** Time Windows

Planned Blood Sampling	Time Windows (min)
Pre-dose	- 60
15, 30, 45 and 60 min post-dose	± 2
90 min, and 2, 3, 4, 6, 8 and 12 h post-dose	± 5
24, 36 and 48 h post-dose	± 15
72 h post-dose	± 30

At visits where assessment time points coincide with each other, the vital signs and ECG assessments should be performed slightly before the specific time point and the PK blood sampling should be performed on time.

Details of blood sample collection, labeling, processing, storage and shipment requirements will be described in a separate laboratory manual. For the amount of blood taken in this study see [Appendix II](#).

All sample handling procedures, including the time of each sample collection, the time of placement into frozen storage (at the end of the sample preparation), and the date of transfer or shipment of the samples to the responsible analyst will be documented in detail.

Concentrations of total dabigatran and tepotinib and its metabolites MSC2571109A and MSC2571107A will be measured using validated liquid chromatography and tandem mass spectrometry (LC-MS/MS) methods at Nuvisan. The assays will be carried out in accordance with GLP regulations and the EMA reflection paper (GCP). A separate bioanalytical protocol will be provided before the start of the analytical part of the study. Full details of the bioanalytical method used will be described in a separate bioanalytical report.

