### **Day 8 to 11 (inpatient)**

Prior to dosing on Day 8 the following will be done:

- Vital signs

- 12-lead ECG
- Blood and urine samples for safety laboratory assessments
- Pre-dose PK blood sample will be taken for determination of total dabigatran, tepotinib and its metabolites and coagulation parameters

After completion of the pre-dose assessments a standardized breakfast will be served and dabigatran etexilate and tepotinib will be administered 30 min after start of breakfast. At 4 h after administration of study drugs the subjects will consume a standardized lunch.

After dosing safety assessments (vital signs, 12-lead ECGs) will be performed regularly and blood samples for determination of total dabigatran and coagulation parameters will be taken (please refer to [Table 2](#)). Prior to discharge on Day 11 blood and urine samples will be taken in addition for safety laboratory assessments. Subjects will be asked regularly about their well-being and any medication taken.

Details about the measurements are provided in Sections [7.4](#) and [7.5.1](#).

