CL _{SS/f}	Apparent total body clearance of drug at steady state following extravascular administration, considering the fraction of dose absorbed. CL _{SS/f} = Dose p.o. / AUC _τ (parent drug only)
C _{max,SS}	Maximum observed plasma concentration during a complete dosing interval at steady state
C _{min,SS}	Minimum observed plasma concentration during a complete dosing interval at steady state
t _{max,SS}	The time to reach the maximum observed plasma concentration collected during a dosing interval (unless otherwise defined, take the 1 st occurrence in case of multiple/identical C _{max} values)
F _{rel,test/reference}	Relative bioavailability, defined as AUC _{0-∞,test} /AUC _{0-∞,reference} ,
	$F = \frac{AUC_{0-\infty, \text{test}}}{AUC_{0-\infty, \text{reference}}} * 100$

Individual PK parameters will be calculated using actual sampling times. The predose sample will be considered as if it had been taken simultaneously with the administration of study drug. PK variables will be evaluated and listed for all subjects who provide sufficient concentration-time data.

Plasma concentrations below LLOQ before the last quantifiable data point will be taken as zero for calculating the AUC (ie, embedded BLQ values set to zero). Plasma concentrations below LLOQ after the last quantifiable data point will not be considered for the determination of λ_z.

The following PK parameters will be calculated for diagnostic purposes and listed, but will not be summarized:

- The time interval (h) of the log-linear regression (λ_{z low}, λ_{z upp}) to determine λ_z.
- Number of data points included in the log-linear regression analysis to determine λ_z.
- Goodness of fit statistic (Rsq) for calculation of λ_z.

The regression analysis should contain data from at least 3 different time points in the terminal phase consistent with the assessment of a straight line on the log-transformed scale. Phoenix WinNonlin best fit methodology will be used as standard. The last quantifiable concentration should always be included in the regression analysis, while the concentration at t_{max} and any <LLOQ concentrations that occur after the last quantifiable data point should not be used.

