The coefficient of correlation (R^2) should be ≥ 0.8 and the observation period over which the regression line is estimated should be at least twofold the resulting $t_{1/2}$ itself. If these criteria are not met, then the corresponding values should be flagged in the listing displaying Individual Plasma Pharmacokinetic Diagnostic Parameters for Each Treatment. Any flags should be included in the study specific SDTM. Then the rate constants and all derived parameters (e.g. $AUC_{0-\infty}$, $\%AUC_{extra}$, CL/f , $t_{1/2}$, and Vz/f) will be included in the parameter listings and will be discussed appropriately in alignment with the protocol lead and quantitative pharmacology representative.

Partial areas AUC_{τ} should be calculated using the scheduled dosing interval, as defined in the Clinical Trial Protocol. The actual dosing interval calculated from eCRF time data should not be used. The following rules apply when calculating the partial area AUC_{τ} within the observed time interval from T_1 to T_2 :

- If the start time of the interval (T_1) occurs before the first observation, the observation at T_1 will be estimated using the linear interpolant between the first datapoint and C_0 . For single dose data $C_0 = 0$ when the drug was administered via an extravascular route. For steady state models, C_0 is the minimum concentration value occurring within the time interval T_1 to T_2 .
- If either T_1 or T_2 falls within the time range in which samples were taken, but does not coincide with an observed data point, then a linear or logarithmic interpolation is performed to estimate the corresponding concentration value. Whether a linear or logarithmic interpolation is used will depend on the method of AUC calculation e.g. linear up log down.
- If the end time of the interval (T_2) occurs after the last measurable concentration and the terminal regression (λ_z) is estimable, then λ_z is used to estimate the concentration at time T_2 . The log trapezoidal rule will be used to calculate the area from the last observation time to the end time of the partial area (T_2). If λ_z cannot be estimated the partial area will not be calculated.

The IMP dose administered is given for the monohydrate hydrochloride salt (ie, 500 mg IMP). A conversion factor for the freebase IMP was calculated and will be applied when 'dose' is used in deriving PK parameter formulas needing a dose value (CL/f).

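### The tepotinib sample that closes the Day 7 profile carries two conflicting time windows, and the SAP does not say clearly how AUCtau is closed at 24 h, so AUCtau can be lost in late-peaking profiles.

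*Protocol*

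**What the plan says.** Protocol Section 7.5.1 defines the sample that ends the Day 7 tepotinib profile as "24 h post-dose (prior to dosing on Day 8, within 60 min prior to administration". Footnote g of Table 2 repeats this.

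Two rows of Table 4, in the same section, could govern the draw: the pre-dose row, which allows 60 min before dosing, and the row "24, 36 and 48 h post-dose ± 15". Samples outside their window "need an explanation and will be considered a protocol violation".

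Protocol Section 7.1.2 (Day 8 to 11) lists the draw among the assessments before dosing: "Pre-dose PK blood sample will be taken for determination of total dabigatran, tepotinib and its metabolites and coagulation parameters". The order is then fixed: "After completion of the pre-dose assessments a standardized breakfast will be served", and both drugs are given 30 min after breakfast starts.

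SAP Section 16.1.5 sets tau to the scheduled 24 h and tells the analyst not to use the actual dosing interval, but it computes individual parameters from actual sampling times. When the interval ends after the last measurable concentration, lambda-z carries the curve to 24 h. If lambda-z "cannot be estimated the partial area will not be calculated". For lambda-z, "The regression analysis should contain data from at least 3 different time points in the terminal phase", and the concentration at tmax is left out. CLss/f is dose over AUCtau, for the parent only.

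Protocol Section 7.5.2 and SAP Section 16.1.5 also treat the pre-dose sample as drawn at the moment of dosing. SAP Section 16.1 gives time 0 h only to pre-dose samples taken before the first administration.

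**The concern.** The draw is named in two ways, as a 24 h sample and as a pre-dose sample, and each name brings its own window. On the planned schedule a site that follows the breakfast order cannot meet the 24 h row.

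The naming also matters for the analysis. If the draw keeps its actual time, the profile stops short of 24 h and the SAP turns to lambda-z. A profile that peaks late has too few later points for that fit, and the stated rule then drops the whole AUCtau although nearly all of the interval was observed. Such losses would depend on profile shape, which sits badly with the assumption in SAP Section 9 that missing data are missing completely at random.

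At stake are AUCtau for tepotinib and two metabolites, and CLss/f for tepotinib, in the first multiple dosing of healthy subjects (Protocol Section 5.2.3). SAP Section 6 also lists tepotinib PK parameters among the data for the evaluation after the first 6 subjects, where one or two missing values would show.

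**Working it through.** **1. One draw or two?** Protocol Appendix II states 14 tepotinib samples. Day 6 pre-dose (1) + Day 7 pre-dose (1) + 12 post-dose times (0.25, 0.5, 0.75, 1, 1.5, 2, 3, 4, 6, 8, 12, 24 h) = 14. The stated figure is reproduced with no separate Day 8 sample, so the 24 h sample and the Day 8 pre-dose sample are the same draw.

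**2. Windows.** Let D be the time of the Day 8 dose in hours after the Day 7 dose.
- Within 60 min before dosing and before breakfast: D - 1.0 to D - 0.5.
- Table 4, 24 h row: 24 ± 0.25 = 23.75 to 24.25 h.
- At D = 24 the draw falls at 23.0-23.5 h, which is 23.75 - 23.5 = 0.25 h to 23.75 - 23.0 = 0.75 h too early (15 to 45 min). The windows do not overlap.
- Without the breakfast order, Section 7.5.1 alone can be met at 23.75-24.0 h.
- The windows overlap if D - 0.5 ≥ 23.75 and D - 1.0 ≤ 24.25, that is, for D from 24.25 to 25.25 h.

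**3. When lambda-z is needed.** On actual times, any last draw before 24.0 h needs it, including one at 23.9 h inside the ±15 min row. A draw after 24.0 h is handled by interpolation.

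**4. Points left after the observed tmax,ss.**
- 6 h: 8 h, 12 h and the closing sample, 3 points, enough.
- 8 h: 12 h and the closing sample, 2 points, too few.
- 12 h: the closing sample, 1 point, too few.

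**5. Quality of a fit that can be made.** The SAP asks for an observation period of at least twice the half-life. At about 30 h (Protocol Section 5.2.3) that is 60 h. A fit from 8 to 23.5 h covers 15.5/30 = 0.52 half-lives. Such fits would be flagged, not deleted.

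**6. Area at issue.** Assume a one-compartment steady-state profile with k = ln 2/30 = 0.0231 per h, tau = 24 h and absorption rates ka from 0.05 to 1.0 per h (assumed; the documents give none). C(t) is proportional to ka/(ka - k) × [exp(-kt)/(1 - exp(-24k)) - exp(-ka·t)/(1 - exp(-24ka))].
- Share of AUCtau after 23.5 h: 1.6-2.0%.
- Share of AUCtau after 23.0 h: 3.2-4.0%.

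**7. Cost of placing the draw at 24 h.** With the linear-up/log-down rule on the protocol's sampling grid, AUCtau rises by 0.13-0.26% (draw at 23.5 h) or 0.25-0.51% (draw at 23.0 h). Hand check for fast absorption and a 23.0 h draw:
- The end value is too high by exp(0.0231) - 1 = 2.3%.
- About half of that passes into the 12-24 h segment.
- That segment holds about (0.758 - 0.574)/(1 - 0.574) = 0.43 of AUCtau.
- 0.5 × 2.3% × 0.43 = 0.5%.

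**The case against.** The strongest reply is that the draw's own sentence states its window, 60 min before dosing, and that Section 7.1.2 calls it a pre-dose sample. It therefore fits the pre-dose row of Table 4 and misses only a general row that also serves the dabigatran profiles. A reader might infer a protocol violation in every subject. The documents do not support that: nothing says the general row overrides the specific sentence, and the clash also needs Day 8 dosing less than 24.25 h after Day 7 dosing, with no dosing-time window given. What stands is that Table 4 does not say which row applies.

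The second reply is that the pre-dose convention already places this draw at the Day 8 dose, hence at 24 h, so lambda-z is never needed. That is a fair reading, but not a secure one. The convention does not mention a sample that closes the previous interval, SAP Section 16.1 limits the 0 h assignment to samples before the first dose, and Protocol Section 7.5.1 says recorded times will be used. Two analysts could reach a value and a missing value from the same profile.

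It is also tempting to say that the breakfast order causes the loss of AUCtau. It does not, because any draw before 24.0 h triggers the rule. The breakfast order only makes an early draw systematic on the planned schedule.

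Finally, the three-point rule is worded as a recommendation, and failing the R-squared or span criterion only flags the values. Both soften the consequence. Neither says how AUCtau is closed when lambda-z is not estimable, other than by omitting it.

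**Conclusion.** The point holds as two linked wording faults.
- **Timing.** With doses 24 h apart and the breakfast order followed, the pre-dose window and the 24 h row of Table 4 cannot both be met; the gap is 15 to 45 min.
- **Analysis.** If actual times apply to this draw, AUCtau can be lost when the observed tmax,ss is 8 h or later, and with it CLss/f for the parent. The unobserved area is about 1.6-4.0% of AUCtau, given a 30 h half-life and the assumed absorption rates.

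A reader might conclude that AUCtau will go missing for many subjects. The documents cannot show this. They give no tmax for tepotinib or its metabolites, so the loss ranges from none (all peaks at 6 h or earlier) to all (all peaks at 8 h or later), and it is nil if the pre-dose convention was meant to cover the draw.

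The endpoints are exploratory and receive summary statistics only. Cmax,ss, Cmin,ss and tmax,ss do not depend on the rule, and the primary dabigatran analysis is unaffected. The change is worth making because it is cheap and removes an ambiguity that could yield different results from the same data.

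**What to change.** - **Protocol.** Reconcile Sections 7.1.2 and 7.5.1 and footnote g of Table 2 with Table 4, by stating in Table 4 that the Day 7 24 h tepotinib sample follows the pre-dose (-60 min) window. The ±15 min row stays for the dabigatran samples.
- **SAP Section 16.1.5.** State that, for tepotinib and both metabolites, the Day 8 pre-dose concentration is used as C(24 h) when calculating AUCtau. AUCtau is then not set to missing for want of lambda-z over the last 0.5-1 h. This extends the existing pre-dose convention to the draw it leaves unclear.

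The cost is one table entry and one sentence, with no extra sample. The downside is an upward bias of about 0.1-0.5% in AUCtau, and a matching downward bias in CLss/f, under the 30 h half-life and assumed absorption rates.
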